5.4.4. Secondary (Global) Analyses

Note: Analysis programs may require independent results verification per CBAR PROG.10033.

The following will be conducted for the three diagnostic tests.

- a. Table: Summary of estimated positive and negative predictive values (PPV and NPV).
- b. Figure: Plot of predictive PPV and NPV estimates as a function of prevalence for each test (point estimates and 95% pointwise confidence bands)
- c. Table/Figure: The 95% Score confidence interval estimates of positive and negative likelihood ratios with forest plot display (one plot per test).
- d. Table/Figure: Sensitivity analyses estimating PPV, NPV, and positive and negative likelihood ratios where indeterminates are: a) counted as all infected, b) all not infected, and c) based on symptom status reported in [SIGNS and SYMPTOMS].

5.4.5. Subgroup Analyses

Note: Analysis programs may require independent results verification per CBAR PROG.10033.

For each of the three diagnostic tests, subgroup analyses will be conducted for males, females, symptomatic participants, and asymptomatic participants by pathogen and anatomic site. The analyses described in Sections 5.4.3 and 5.4.4 will be conducted for each group.

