6.6.2 Secondary Analyses

Global Analyses

For each diagnostic test:

- Positive and negative predictive values (PPV and NPV) will be estimated. PPV and NPV will each be plotted as a function of prevalence (point estimates and 95% pointwise confidence bands)
- Positive and negative likelihood ratios will be estimated using 95% Score confidence intervals
- A sensitivity analysis will include calculating equivocal predictive values and likelihood ratios
- An additional sensitivity analysis will calculate PPV, NPV, and positive and negative likelihood ratios for the sensitivity analyses where indeterminates are counted as Infected and Not Infected

Subgroup Analyses

For each of the three diagnostic tests, subgroup analyses will be conducted for males, females, symptomatic participants, and asymptomatic participants by pathogen and anatomic site. The 95% Score confidence interval estimates of PPA and NPA will be displayed using forest plots (one plot per test). The 95% Score confidence interval estimates of positive and negative likelihood ratios will be displayed using forest plots (one plot per test). PPVs and NPVs will each be plotted as a function of prevalence (point estimates and pointwise confidence bands).

The sensitivity analyses where indeterminates are counted as Infected and Not Infected will be repeated for the four subgroup analyses.

Exploratory Analysis

Developing methods for diagnostic benefit:risk analyses (e.g., diagnostic yield) will be applied.

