1.2.1. Global analyses

For each NAAT under evaluation, positive predictive values (PPVs), negative predictive values (NPVs), positive likelihood ratios, and negative likelihood ratios will be calculated for detection of the organism and extragenital site combinations listed below.

- *Neisseria gonorrhoeae* in rectal swabs
- *Neisseria gonorrhoeae* in pharyngeal swabs
- o Chlamydia trachomatis in rectal swabs
- Chlamydia trachomatis in pharyngeal swabs
- 1.2.2. Subgroup analyses

For each NAAT under evaluation, to estimate the PPAs, NPAs, PPVs, and NPVs for detection of NG and CT from rectal and pharyngeal swab specimens by sex and by anatomic site-specific symptom status.

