 - Table 11 and Table 12: Company 2 Assay (Company 2) and Company 3 Assay (Company 3).
 - Table 13 and Table 14: Company 1 Assay (Company 1) and Company 3 Assay (Company 3).
- h. Figure: Plot of PPA and 95% confidence interval band versus proportion of indeterminate ASIS results assumed to be positive (range of 0 to 1); vice-versa for NPA plot.
- i. Table: Using Fischer's exact test, the association between test results and randomized swab order will be examined. Associations will be conducted by anatomical site and organism combination.

Table 11: Result of Test under Consideration versus ASIS: Company 2 Assay (Company 2) and Company 3 Assay (Company 3)

		ASIS			
		Infected	Indeterminate	Not infected	
	Positive	A	D	G	
Result of Test under Consideration	Equivocal	В	E	Н	
	Negative	С	F	I	
	No result	Exclude from analysis ¹			
¹ Note: If the test under consideration has "no result" because the test was not run and no attempt was made to test the sample, the					

test result will be excluded from primary analysis. If the ASIS result is invalid, this result will be excluded from the primary analysis.

Table 12: Calculation of the positive and negative percent agreement: Company 2 Assay (Company 2) and Company 3 Assay (Company 3)

Analysis Type	PPA	NPA		
Primary Analysis	A / (A+B+C +F)	l / (G+H+l + D)		
Sensitivity Analysis Scenarios				
Classify indeterminates ¹ using symptom status reported	A / (A+B+C+F)	I / (G+H+I+D)		
from [SIGNS AND SYMPTOMS]				
Include all indeterminate tests as infected.	(A+D) / (A+B+C+D+E+F)	l / (G+H+I)		
Include all indeterminate tests as not infected.	A / (A+B+C)	(I+F) / (D+E+F+G+H+I)		
Consider indeterminate and equivocal test results as "missing", with the assumption of missing at random, and model the missing results. ²	A / (A+C)	l / (G+l)		
Classify indeterminate tests on the basis of symptom status. Include indeterminate tests as Infected if the participant is symptomatic in that compartment; include indeterminate tests as not infected in the participant is asymptomatic in that compartment. Cells B, D, E, F and H will be assigned or weighted to cells A, C, G and I based on modeling of the missing results.				

Table 13: Result of Test under Consideration versus ASIS: Company 1 Assay (Company 1) and Company 3 Assay (Company 3)

		ASIS			
		Infected	Indeterminate	Not infected	
	Positive/Detected	A	С	E	
Result of Test under Consideration	Negative/Not detected	В	D	F	
	No result	Exclude from analysis ¹			

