Note: If the test under consideration has "no result" because the test was not run and no attempt was made to test the sample, the					

¹ Note: If the test under consideration has "no result" because the test was not run and no attempt was made to test the sample, the test result will be excluded from primary analysis. If the ASIS result is invalid, this result will be excluded from the primary analysis.

Table 14: Calculation of the positive and negative percent agreement: Company 1 Assay (Company 1) and for the Company 3 Assay (Company 3)

Analysis Type	PPA	NPA
Primary Analysis	A / (A+B +D)	F / (C+E +F)
Sensitivity Analysis Scenarios		
Classify indeterminates ¹ using symptom status reported from [SIGNS AND SYMPTOMS]	A / (A+B+D)	F / (C+E+F)
Include all indeterminate tests as infected.	(A+C) / (A+B+C+D)	F / (E+F)
Include all indeterminate tests as not infected.	A / (A+B)	(D+F) / (C+D+E+F)
Consider indeterminate and equivocal test results as "missing", with the assumption of missing at random, and model the missing results. ²	A / (A+B)	F / (E+F)

¹ Classify indeterminate tests on the basis of symptom status. Include indeterminate tests as Infected if the participant is symptomatic in that compartment; include indeterminate tests as not infected in the participant is asymptomatic in that compartment.
² Cells C and D will be assigned or weighted to cells A, B, E and F based on modeling of the missing results.

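### SAP 5.4.5 carries the symptom-status rule for indeterminates into the symptom subgroups, where it gives the two groups opposite reference rules and can create a difference from identical data

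*SAP*

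**What the plan says.** SAP 1.2.2 makes accuracy "by sex and by anatomic site-specific symptom status" a secondary objective. SAP 5.4.5 names four subgroups (males, females, symptomatic, asymptomatic) and states: "The analyses described in Sections 5.4.3 and 5.4.4 will be conducted for each group". It exempts nothing.

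SAP 5.4.3, Tables 12 and 14, includes a sensitivity row that classifies indeterminates by reported symptoms. The footnote to each table gives the rule: "Include indeterminate tests as Infected if the participant is symptomatic in that compartment", and "include indeterminate tests as not infected in the participant is asymptomatic in that compartment" (reading the second *in* as *if*). SAP 5.4.4(d), option c, applies the same classification to PPV, NPV and the likelihood ratios, with no formula.

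The formulas printed on the symptom-status rows for PPA are A/(A+B+C+F) in Table 12 and A/(A+B+D) in Table 14. Both are identical to the primary-analysis row above them.

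Protocol 6.6.1 lists the symptom-status classification among the sensitivity analyses. For subgroups, however, Protocol 6.6.2 names only two: "The sensitivity analyses where indeterminates are counted as Infected and Not Infected will be repeated for the four subgroup analyses".

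**The concern.** The variable that defines the subgroup also decides how its indeterminates are classified. In the whole study population, or within one sex, the rule moves some indeterminates each way. Within a symptom subgroup it moves all of them the same way, and in opposite directions for the two groups. A difference between symptomatic and asymptomatic participants on that row can therefore come from the rule and not from the assay.

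The row also adds nothing. In symptomatic participants it equals the all-infected row, and in asymptomatic participants it equals the all-not-infected row. Both are already tabulated for each subgroup. What is at stake is a misleading contrast on a stated secondary objective, in PPA and, through 5.4.4(d), in PPV and the likelihood ratios.

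**Working it through.** **Plan's own figure.** The documents state no subgroup gap, indeterminate rate or share of indeterminates that test positive. The only PPA calculation is in Protocol 6.3, and the 96% used below comes from there. With p0 = 0.90 and p1 = 0.96, n = [(1.960·√(p0(1-p0)) + z_power·√(p1(1-p1)))/(p1-p0)]² gives 157.5, 173.8 and 195.6 for 80%, 85% and 90% power, against the stated 157, 174 and 196. It reproduces within rounding.

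**What the footnote becomes (Table 14 cells).** A and B are test-positive and test-negative among infected, C and D among indeterminate, E and F among not infected.

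- Symptomatic subgroup: PPA = (A+C)/(A+B+C+D), which is the all-infected row.
- Asymptomatic subgroup: PPA = A/(A+B), which is the all-not-infected row.
- Printed formula: PPA = A/(A+B+D) in both.

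**Gap from identical data.** Give each group n infected with PPA p, and k indeterminates of which a share s test positive. Symptomatic PPA is (np+ks)/(n+k) and asymptomatic PPA is p, so

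gap = (np+ks)/(n+k) - p = k(s-p)/(n+k).

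The same formula holds for Table 12, with equivocal readings counted as not positive. The values of n, k and s are assumptions; p = 96%. Gap in percentage points, symptomatic minus asymptomatic:

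| n infected | k | s = 1 | s = 0.5 | s = 0 |
|---|---|---|---|---|
| 100 | 2 | +0.1 | -0.9 | -1.9 |
| 100 | 5 | +0.2 | -2.2 | -4.6 |
| 100 | 10 | +0.4 | -4.2 | -8.7 |
| 50 | 2 | +0.2 | -1.8 | -3.7 |
| 50 | 5 | +0.4 | -4.2 | -8.7 |
| 157 | 5 | +0.1 | -1.4 | -3.0 |

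The gap is zero when s = p. At n = 100, a 3-point gap needs about 7 indeterminates if half test positive, or about 3 if none do.

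**One worked table.** Take A=96, B=4, C=5, D=5, E=10, F=990 in both groups.

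- PPA: 101/110 = 91.8% symptomatic, 96/100 = 96.0% asymptomatic; gap -4.2.
- PPV, taken directly from the cells: 101/111 = 91.0% against 96/111 = 86.5%; gap +4.5, the opposite direction.
- NPA: 990/1000 = 99.0% against 995/1010 = 98.5%; gap +0.5. With 1,000 not infected at 99% and k up to 10, the NPA gap is at most about 1 point.
- Negative likelihood ratio: (9/110)/0.990 = 0.083 against 0.040/0.985 = 0.041, about twofold.
- Positive likelihood ratio: 0.918/0.010 = 91.8 against 0.960/(15/1010) = 64.6.
- Printed symptom-status formula: 96/105 = 91.4% in both groups; no gap.

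**Under one common rule.** The same cells give 91.4% (primary), 91.8% (all infected) or 96.0% (all not infected) in both groups. The contrast disappears.

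**The case against.** Five points can fairly be made against the concern.

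First, a reader might infer that identical data will show a PPA gap of several points. The documents do not support that, because they give neither k nor s. Every indeterminate row of SAP Table 4 needs at least one equivocal or no-result reading; plain discordance settled by a positive or negative tiebreaker is never indeterminate. The Company 1 assay has no equivocal result, nor does the Company 3 assay for NG. Indeterminates may be few. This stands, so the size can only be given as a range.

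Second, a reader might infer that PPA will always look worse in symptomatic participants. That holds only when s is below p, and PPV can move the other way. This also stands.

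Third, if the printed row formulas are programmed there is no gap. That is true, but the row is then a mislabelled copy of the primary analysis that uses no symptom data, and 5.4.4(d) option c has only the verbal rule to follow. The mismatch is a second defect and does not remove the first.

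Fourth, the damage is contained. No formal comparison of symptomatic with asymptomatic participants is planned. Neither document says that the symptom-rule PPA goes into a forest plot. The common-rule rows appear for both groups, and the plot in 5.4.3(h), repeated by subgroup, allows comparison at any shared fraction of indeterminates. All of this stands and limits the weight of the point.

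Fifth, Protocol 6.6.2 already names only the two common-rule analyses for subgroups. That locates the fault in the SAP's cross-reference and supports the fix.

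**Conclusion.** The point holds as a defect in one sensitivity scenario. Read as written, SAP 5.4.5 puts the symptom-status rule into the two subgroups where it yields opposite reference rules and duplicate rows, and it goes beyond what Protocol 6.6.2 names. The PPA artefact is k(s-p)/(n+k). In the cases tabulated above it runs from about zero, or slightly positive, to almost 9 points negative. It arises only if the footnote is programmed and not the printed formula.

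A reader might take this to undermine the subgroup results as a whole. It does not: the primary subgroup PPA and NPA use the same formula in both groups and are untouched, as are the all-infected and all-not-infected rows.

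**What to change.** Add one sentence to SAP 5.4.5: in the symptomatic and asymptomatic subgroups the symptom-status scenario (Tables 12 and 14, and 5.4.4(d) option c) is omitted, and the primary, all-infected and all-not-infected analyses are shown for both. Keep the scenario for the overall and sex analyses, where it is not degenerate.

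Correct the symptom-status rows to match their footnote. With subscript s for indeterminates in participants symptomatic at that site and a for asymptomatic:

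- Table 12: PPA = (A+Ds)/(A+B+C+Ds+Es+Fs); NPA = (I+Fa)/(G+H+I+Da+Ea+Fa).
- Table 14: PPA = (A+Cs)/(A+B+Cs+Ds); NPA = (F+Da)/(E+F+Ca+Da).

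The cost is one sentence and two table rows. There are fewer outputs, and no information is lost, because each omitted result equals one that is kept.

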5.5. Exploratory Analyses

Application of methods for diagnostic benefit:risk analyses will be conducted, including BED-FRAME methodologies¹⁰. Analyses related to these objectives will be initiated upon completion of primary analyses.

¹⁰ Evans, S.R., Pennello, G., Pantoja-Galicia, N., Jiang, H., Hujer, A.M., Hujer, K.M., Manca, C., Hill, C., Jacobs, M.R., Chen, L. and Patel, R., 2016. Benefit-risk evaluation for diagnostics: a framework (BED-FRAME). Clinical Infectious Diseases, p.ciw329.

H. APPENDIX 1: CBAR SOP PROG.10033

Center for Biostatistics in AIDS Research (CBAR)				
STANDARD OPERATING PROCEDURE				
Title: Application Validation				
Document ID: PROG.10033	Document Version: 4			
	Page 23 of 27			

1. Purpose

This document provides procedures for validation of programs and applications developed at CBAR as part of work on clinical studies.

2. Scope and Applicability

This document is applicable to programs and applications developed and used by CBAR workforce members in conjunction with work with data from clinical studies.

3. Introduction

Validation of programs and applications used at CBAR to create or analyze datasets in conjunction with clinical studies ensures that analysis results accurately reflect the original source data and conform to analysis specifications. Using a risk-based approach to validation, CBAR has developed standard operating procedures (SOPs) that define minimum programming standards for coding, testing and validation for the range of programming applications used at CBAR. This document provides a reference to the specific programming standards that apply to specific types of programs or applications and outlines procedures for documenting their validation.

4. Definitions

- **CBAR program:** Any of the various types of programs or applications that are created and maintained by the CBAR Programming Core for use across CBAR for the purpose of creating reports, files, or SAS datasets with minimal input from users. This includes SAS table and format programs and reporting macros as well as UNIX and R packages (e.g., MAKETOX2 and the PIPS library of functions).
- CBAR derived dataset program: A program, created and maintained by the CBAR Programming Core, that creates one or more standardized derived datasets for use across CBAR, which does not represent a single CRF or codebook at the DMC.
- CBAR macro: A generic SAS macro, created and maintained by the CBAR Programming Core, that consists
 of flexible SAS code that can be easily tailored to individual studies for reporting purposes (i.e., CBAR reporting
 macro) or perform simple operations similar to SAS functions (i.e., CBAR autocall macro).
- **CBAR R program:** An R program used by a CBAR R package created or maintained by members of the CBAR Programming Core.
- **CBAR SAS format program:** A program, created and maintained by the CBAR Programming Core, that creates permanent SAS (in)format(s) for the CBAR format catalog.
- **CBAR SAS template program:** A program, created and maintained by the CBAR Programming Core, that defines one or more SAS ODS templates (e.g., a style template, ExcelXP tagset, or graphic template).
- **CBAR UNIX package:** A collection of UNIX programs and other files, created and maintained by members of the CBAR Programming Core, for use across CBAR for the purpose of creating reports, files, or SAS datasets with minimal input from users. This includes all modules included by the main executable program file. For example, the MAKE_SMR UNIX package contains the MAKE_SMR file, smr.sas, and all of the macro program files included by smr.sas, and the MAKEDATA downloading scripts are part of a CBAR UNIX Package.
- CBAR UNIX program: A UNIX shell script, created and maintained by members of the CBAR Programming Core, comprised of all modules utilized by the executable program file for use across CBAR for the purpose of creating reports, files, or SAS datasets with minimal input from users. For example: Both MAKEDATA and MAKEDATA_NOSTUDY are both CBAR UNIX programs within the CBAR UNIX package MAKEDATA.

- Clinical Study: A clinical trial or observational study involving human subjects.
- **Miscellaneous CBAR Program:** A program or application, created and maintained by the CBAR Programming Core, that does not fall under the definition of any of the CBAR programs in Section 5.0 of PROG.10033 Application Validation.
- **SAS table program:** A SAS program, created and maintained by the CBAR Programming Core, which creates one or more SAS datasets from ASCII data to represent a single CRF or codebook from the DMC.
- Workforce members: Employees (both academic appointees and staff), and other persons whose conduct, in the performance of CBAR work is under the direct control of CBAR whether or not they are paid by Harvard University.

5. Procedure

The following table outlines the different types of programs or applications based on their intended purposes and programming language. The table provides the CBAR SOP that defines the relevant programming standards for the development, testing, and validation of the program or application as well as the appropriate validation form that documents the validation process.

Formal validation of programs and applications not covered by the scope of relevant programming standards SOP is not required, but adherence to the practices described therein (as appropriate) is recommended.

Development, testing, and validation standards of CBAR programs and applications of a type not covered in the table below (miscellaneous CBAR programs) are at the discretion of the Head of the CBAR Programming Core. Validation review of these programs consists of 5 areas of focus: Source Code Control, Supporting Documentation, Program Code Review, Program Logic Review, and Testing Program Review, including Input and Output. Specific criteria within each of the 5 areas are at the discretion of the validation reviewer and are approved by the Head of the CBAR Programming Core.

Type of Program/ Application	Programming Standards SOP	Validation Form	Personnel to be Notified upon Completion of Validation
Study-Specific Derived Dataset Creation Programs (including format and macro programs)	PROG.10066 Study- Specific Derived Dataset Creation Programming Standards	PROG.10066.f1 Study- Specific Derived Dataset Creation Programming Review	Programmer
Study-Specific Analysis programs (including macro, template, and R programs)	PROG.10067 Study- Specific Analysis Programming Standards	PROG.10067.f1 Study- Specific Analysis Programming Review	Programmer
Study-Specific Fix Files	PROG.10030 Study- Specific Fix File Programming Standards	PROG.10030.f1 Study- Specific Fix File Programming Standards	Programmer
Study-Specific User Options Files	PROG.10071 Study- Specific User Options File Standards	PROG.10071.f1 Study- Specific User Options File Review	Programmer
SAS Table Programs	PROG.10029 SAS Table Programming Standards	PROG.10029.f1 SAS Table Programming Review	None
CBAR Derived Dataset Programs	PROG.10035 SAS Derived Dataset Programming Standards	PROG.10035.f1 SAS Derived Dataset Programming Review	Programmer, cbar.cda
CBAR SAS Format Programs	PROG.10037 SAS Format Programming Standards	PROG.10037.f1 SAS Format Programming Review	None
CBAR Macros	PROG.10034 SAS Macro Programming Standards	PROG.10034.f1 SAS Macro Programming Review	Programmer, head of CBAR programming core

UNIX Programs	PROG.10031 UNIX Package Programming Standards	PROG.10031.f1 UNIX Package Programming Review	Programmer, head of CBAR programming core
CBAR R Programs	PROG.10036 R Programming Standards	PROG.10036.f1 R Programming Review	Programmer, head of CBAR programming core
CBAR SAS Template Programs	PROG.10038 SAS Template Programming Standards	PROG.10038.f1 SAS Template Programming Review	Programmer, head of CBAR programming core

5.1 Validation Form Submission

The completed and signed validation form is submitted to Document Management within 5 days of validation completion in one of the following ways:

- Place the form in the Document Management mailbox; or
- Mail the form to Document Management at CBAR; or
- Contact Document Management to arrange another method of submitting the signed form.

In the event that completion and signing of the validation form conflicts with the analysis reporting timeline, notification of validation completion may be documented via email to the required personnel. In this case, submission of the completed validation form to Document Management at CBAR occurs within 5 business days of distribution of the analysis report.

For the validation of miscellaneous CBAR programs, the validation criteria are submitted with the validation form.

5.2 Content of PROG.10033.f1 Miscellaneous CBAR Programming Review

- Program name and location
- Last date in change history
- Coding programmer
- Validation reviewer
- Head of the CBAR Programming Core
- Date of validation
- Version of PROG.10033 Application Validation used
- Miscellaneous CBAR Program Review
 - Review Criteria
 - Finding(s) during review
 - Resolution(s) prior to validation
- Signature of validation reviewer
- Date of signature
- Signature of Head of the CBAR Programming Core
- Date of signature

Referenced Documents

Document Title	Location
PROG.10029 SAS Table Programming Standards	Secure location on the CBAR network
PROG.10029.f1 SAS Table Programming Review	Secure location on the CBAR network
PROG.10030 Fix File Programming Standards	Secure location on the CBAR network
PROG.10030.f1 Fix File Programming	Secure location on the CBAR network

PROG.10031 UNIX Programming Standards	Secure location on the CBAR network
PROG.10031.f1 UNIX Programming Review	Secure location on the CBAR network
PROG.10033.f1 Miscellaneous CBAR Programming Review	Secure location on the CBAR network
PROG.10034 SAS Macro Programming Standards	Secure location on the CBAR network
PROG.10034.f1 SAS Macro Programming Review	Secure location on the CBAR network
PROG.10035 SAS Derived Dataset Programming Standards	Secure location on the CBAR network
PROG.10035.f1 SAS Derived Dataset Programming Review	Secure location on the CBAR network
PROG.10036 SAS Template Programming Standards	Secure location on the CBAR network
PROG.10036.f1 SAS Template Programming Review	Secure location on the CBAR network
PROG.10037 SAS Format Programming Standards	Secure location on the CBAR network
PROG.10037.f1 SAS Format Programming Review	Secure location on the CBAR network
PROG.10038 R Programming Standards	Secure location on the CBAR network
PROG.10038.f1 R Programming Review	Secure location on the CBAR network
PROG.10066 Study-Specific Derived Dataset Creation Programming Standards	Secure location on the CBAR network
PROG.10066.f1 Study-Specific Derived Dataset Creation Programming Review	Secure location on the CBAR network
PROG.10067 Study-Specific Analysis Programming Standards	Secure location on the CBAR network
PROG.10067.f1 Study-Specific Analysis Programming Review	Secure location on the CBAR network
PROG.10071 Study-Specific User Options File Standards	Secure location on the CBAR network
PROG.10071.f1 Study-Specific User Options File Review	Secure location on the CBAR network

Version History

Version	Changes Made	Effective Date
1	Original Version	12/1/2013
2	Rationale:This version redefines Section 7. Version History to provide more information about the reason for the new version and the major changes included. This also more clearly describes the scope, procedure, and other parts of the SOP.Purpose, Scope, Introduction, Definitions, Section 5: Clarification of language to better describe the scope and procedure; updating of outdated information and removal of unused definitions Section 7: Format of section was changed	12/1/2013

3	Purpose, Scope, and Introduction: Updated to clarify the rationale for	7/1/2014
5	validation and better define how the programming standards and	111/2017
	validation and better denne now the programming standards and validation procedure work together.	
	Definitions:	
	- The definition of CBAR program has been updated	
	- A new definition of a clinical study has been added.	
	Table: Minor changes to table headings	
	5.0 Procedure:	
	- Minor modifications to improve clarity	
	- Addition of standards to be defined by Head of Programming	
	Core for CBAR programs not otherwise covered by current	
	standards	
	 Notification of programmer and cbar.cda for SAS Table 	
	programs and SAS format programs have been removed	
	5.1 Validation Form Submission	
	- Order of the sequence of events changed to clarify that	
	submission of the validation form occurs for the validation to be	
	considered complete	
	- Time-frame for validation document submission removed since,	
	per SOP, it is required for validation completion	
	 Flexibility is provided for validation form completion in the case 	
4	of time-constraints	10/1/0015
4	Rationale: The updates made to this SOP for this version detail	12/1/2015
	validation procedures for miscellaneous CBAR programs.	
	Definitions:	
	- Added definition of Miscellaneous CBAR program	
	5.0 Procedure:	
	 Added description of the validation review of miscellaneous 	
	CBAR programs	
